1.1 ISO 15197:2013 Objective – Accuracy in People with Diabetes

Let MeterBG = meter blood glucose result;

LabBG = laboratory method (YSI) comparator blood glucose result.

$$D = \text{MeterBG} - \text{LabBG}$$

$$RD = 100 * (\text{MeterBG} - \text{LabBG}) / \text{LabBG}$$

Assume 315 evaluable results from people with diabetes. The ISO 15197:2013 acceptance criterion is that 95% of those evaluable results must satisfy the accuracy criteria:

$$|D| = |\text{MeterBG} - \text{LabBG}| \leq 15 \text{ mg/dL}, \text{ for } \text{LabBG} < 100 \text{ mg/dL}$$

or

$$|RD| = 100 * |\text{MeterBG} - \text{LabBG}| / \text{LabBG} \leq 15\%, \text{ for } \text{LabBG} \geq 100 \text{ mg/dL}.$$

With $n = 315$, $X_c = 300$ results would be required to satisfy the accuracy criteria. At $P_0 = 96.79\%$, there is approximately a 95% chance of satisfying the ISO objective. Conversely, at $P_a = 92.77\%$, there is approximately a 95% chance of failing to satisfy the ISO objective.

1.2 FDA Objective – Accuracy with All Subjects Included

For the FDA accuracy objective, a result (MeterBG) is considered accurate if:

$$|RD| = 100 * |\text{MeterBG} - \text{LabBG}| / \text{LabBG} \leq 15\%, \text{ regardless of the value of LabBG.}$$

Assuming $n = 350$ evaluable results, $X_c = 333$ results would be required to satisfy the accuracy criteria. At $P_0 = 96.65\%$, there is approximately a 95% chance of satisfying the FDA 15% objective. Conversely, at $P_a = 92.81\%$, there is approximately a 95% chance of failing to satisfy the FDA accuracy objective.

The FDA guidance has a second criterion, that 99% of n evaluable results must have $|RD| \leq 20\%$. Inasmuch as the two criteria are considered separately, there is no consideration for multiplicity. For the $n = 350$, the 20% criterion requires a critical value of $X_c = .99 * 350$

$= 346.5 \rightarrow 347$. For this critical value and sample size, with $P_0 = 99.61\%$, there is approximately a 95% chance of satisfying the FDA 20% criterion. Conversely, there is approximately a 95% chance of failing to satisfy the 20% criterion if the chance of obtaining a result within $\pm 20\%$ of corresponding comparator measurement is only 97.8%.

Note that each glucose result obtained with the evaluation device will be considered either 'accurate' or 'not accurate', where accuracy depends on the particular test criterion.

1.3 Internal Objective

For subjects with diabetes only (PWDs):

The criterion is defined to be:

$|D| \leq 12.5 \text{ mg/dL}$ if $\text{LabBG} < 100\text{mg/dL}$, or:

$|RD| \leq 12.5\%$ if $\text{LabBG} \geq 100\text{mg/dL}$

The hypothesis:

$$H_0: \Pr\{\text{criterion met}\} < 95\%$$

will be tested against the alternative:

$$H_1: \Pr\{\text{criterion met}\} \geq 95\%$$

With $n = 315$, the critical value is $X_c = 294$ yields a power to reject H_0 if $\Pr\{\text{criterion met}\} = 0.95$ is $\sim 92.63\%$.

Table 1.1 summarizes the power statements made in 1.1, 1.2, and 1.3.

Table 1.1 Power Statements for ISO and FDA Acceptance Criteria

Criterion	N	Xc	Po*	Pr{PASS Po}	Pa**	Pr{FAIL Pa}	
ISO	315	300	96.79%	95.02%	92.77%	94.95%	
±12.5	315	294	95.00%	92.63%	90.60%	94.64%	
FDA-15%	350	333	96.65%	95.00%	92.81%	94.95%	
FDA-20%	350	347	99.61%	95.05%	97.80%	95.00%	

*Po is the minimum required (hypothetical) probability that any measurement would meet the definition of an "accurate" result, in order to have approximately a 95% chance that at least Xc out of N results would be "accurate" (PASS)

**Pa is the maximum required (hypothetical) probability that any measurement would meet the definition of an "accurate" result, in order to have approximately a 95% chance that fewer than Xc out of N results would be "accurate" (FAIL)

In general, critical values depend on actual sample size. The sample size and associated critical values for accuracy tests (the minimum required numbers of "accurate" results) are determined by regulatory guidance. The values of Po and Pa are affected by actual sample size.

2. Blood Glucose Measurements

Some data analysis follows analyses and presentations described in ISO Section 15197:2013, Section 8. See Table 3 for scheme of data analysis, including capillary blood and venous blood.

Other data analysis follows analyses and presentations described in the FDA 2018 OTC Guidance. See Table 4 for scheme of FDA 2018 OTC data analysis, including capillary blood and venous blood.

Blood glucose measurements will all be made in units of mg/dL. Graphs (other than error grids) involving blood glucose concentrations will be constructed in both mg/dL and mmol/L (for ISO analyses; analyses for FDA reporting will include tables and graphs in mg/dL only). The conversion of $X \text{ mg/dL}$ to $Y \text{ mmol/L}$ will be as follows:

$$Y \text{ mmol/L} = \frac{X \text{ mg/dL}}{18.016}$$

Linear regression will be performed on data comparisons as shown in Tables 6.1 and 6.2.

Modified Bland-Altman Plots – Modified Bland-Altman plots (difference between evaluation device results and reference results plotted against reference results) will be constructed for all comparisons described in Tables 6.1 and 6.2.

3. Accuracy Analyses

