3.1 ISO Objective

At least 95% of the glucose results obtained using the evaluation device must be accurate, namely:

$$-15\% \leq RD \leq +15\% \quad \text{LabBG} \geq 100\text{mg/dL}$$

OR

$$-15\text{mg/dL} \leq D \leq +15\text{mg/dL} \quad \text{LabBG} < 100\text{mg/dL}$$

As discussed in section 0 (Sample Size), with $n = 315$, the critical number (minimum) of accurate results is 300, which yields approximately a 95% chance of satisfying the ISO objective criterion if the actual probability that any result will be accurate is at least 96.79%. Symbolically, the ISO criterion is equivalent to testing the hypothesis:

$$H_0 : \text{Prob}\{\text{accurate}\} < 96.79\%$$

versus the alternative:

$$H_1 : \text{Prob}\{\text{accurate}\} \geq 96.79\%$$

There is approximately a 95% chance that the null will NOT be rejected if the actual probability that a result with the evaluation device would satisfy this definition of accuracy is only about 92.76%.

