3.4 Internal Accuracy Objective

The criterion is defined to be:

$|D| \leq 12.5 \text{ mg/dL}$ if $\text{LabBG} < 100 \text{ mg/dL}$, or:

$|RD| \leq 12.5\%$ if $\text{LabBG} \geq 100 \text{ mg/dL}$

The hypothesis:

$$H_0: \Pr\{\text{criterion met}\} < 95\%$$

will be tested against the alternative:

$$H_1: \Pr\{\text{criterion met}\} \geq 95\%$$

With $n = 350$, the critical value is $X_c = 327$ yields a power to reject H_0 if $\Pr\{\text{criterion met}\} = 0.95$ is ≈ 0.9246 .

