7.1 Questionnaire 1 – Ease of Use

Subject questionnaire 1 will consist in part of questions/statements for which a numerical score or rating (1=strongly disagree, 2=disagree, 3=neutral, 4=agree, 5=strongly agree) will be provided by the subjects and entered by the study staff. For these numerically-scored questions, frequency distributions will be tabulated. For PWD subjects only (ISO 15197:2013 requirements), hypothesis tests for selected statements will be performed. The hypotheses are:

$$H_0: \Pr\{\text{response} \geq 3\} < 90\% \text{ versus the alternative:}$$

$$H_a: \Pr\{\text{response} \geq 3\} \geq 90\%$$

The critical number of responses greater than or equal to 3, X_c , is a function of the actual sample size, and will be chosen such that $0.95 = \sup \Pr\{X \geq X_c | 100p\% = 90\%\}$. For example, if $n = 315$, then $X_c = 276$, so that $\Pr\{X \geq X_c | 100p\% = 90\% \} \approx 0.9299 \leq 0.95$. That is, 276 is the number of responses ≥ 3 which yields the largest value of $\Pr\{X \geq X_c | 100p\% = 90\% \} \leq 0.95$ for $n = 315$.

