11.1 Primary Objective, 2.1.1, and Secondary Objectives 2.2.1, 2.2.2 (ISO 15197)

The percentages of results from PWD subjects satisfying the ISO 15197 accuracy definition:

95% of glucose results shall fall within $\pm 15\text{mg/dL}$ of laboratory method (LabBG) at glucose concentration $<100\text{ mg/dL}$ and within $\pm 15\%$ at glucose concentrations $\geq 100\text{ mg/dL}$

will be computed.

If $n = 315$ PWD subjects (90% of 350), the critical value is $0.95*315 = 299.25 \approx 300$. Thus, the critical value is associated with testing the hypothesis:

H0: $\text{Pr}\{\text{ISO Accurate result}\} < 0.9678$

against the alternate:

H1: $\text{Pr}\{\text{ISO Accurate result}\} \geq 0.9678$

(Pardo, 2014)⁵

The power to reject H0 at $\text{Pr}\{\text{ISO Accurate result}\} = 0.9678$ is approximately 0.9490.

Other Secondary Accuracy Objectives

Internal Accuracy Objectives: 2.2.8, 2.2.9

2.2.8 Criterion 1

Define criterion 1:

T-Plus Meter result with $\pm 12.5\text{mg/dL}$ if $\text{LabBG} < 100\text{mg/dL}$, or

T-Plus Meter result within $\pm 12.5\%$ of corresponding Lab result (LabBG), if $\text{LabBG} \geq 100\text{mg/dL}$

Test the hypothesis:

H0: $p = \text{Pr}\{\text{meter result satisfies criterion 1}\} < 0.95$

H1: $p = \text{Pr}\{\text{meter result satisfies criterion 1}\} \geq 0.95$

The critical value, X_c (minimum number of X “successes”) is determined to be the smallest number such that $\text{Pr}\{X \geq X_c | p=0.95\} \leq 0.95$. For $n = 315$, $X_c = 294$ (power ≈ 0.9263).

2.2.9 Criterion 2

Define criterion 2:

T-Plus Meter result with $\pm 15\text{mg/dL}$ if $\text{YSI} < 100\text{mg/dL}$, or

T-Plus Meter result within $\pm 15\%$ of corresponding YSI result, if $\text{YSI} \geq 100\text{mg/dL}$

Test the hypothesis:

H0: $p = \text{Pr}\{\text{meter result satisfies criterion 2}\} < 0.95$

H1: $p = \text{Pr}\{\text{meter result satisfies criterion 2}\} \geq 0.95$

⁵ Pardo, S., (2014) Equivalence and noninferiority Testing for Quality, Manufacturing, and Test Engineers, Chapman&Hall/CRC, Boca Raton

The critical value, X_c (minimum number of X “successes”) is determined to be the smallest number such that $\Pr\{X \geq X_c | p=0.95\} \leq 0.95$. If $n = 315$, $X_c = 294$ (power ≈ 0.9263). If $n = 350$, $X_c = 327$ (power ≈ 0.9246)

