11.2 Secondary Objectives 2.2.4, 2.2.5 (FDA SMBG:2018)

- a. At least 95% of n results will fall within $\pm 15\%$ of the corresponding YSI result
- b. At least 99% of n results will fall within $\pm 20\%$ of the corresponding YSI result

These criteria, with $n = 350$, are equivalent to testing the hypotheses:

$$H_0: \Pr\{\text{T-Plus meter result within } \pm 15\% \text{ of LabBG}\} < 0.9664$$

$$H_1: \Pr\{\text{T-Plus meter result within } \pm 15\% \text{ of LabBG}\} \geq 0.9664$$

with $\Pr\{\text{reject } H_0 | p=0.9664\} \approx 0.9488$

and:

$$H_0: \Pr\{\text{T-Plus meter result within } \pm 20\% \text{ of LabBG}\} < 0.9960$$

$$H_1: \Pr\{\text{T-Plus meter result within } \pm 20\% \text{ of LabBG}\} \geq 0.9960$$

with $\Pr\{\text{reject } H_0 | p=0.9960\} \approx 0.9466$

11.3 Non-Accuracy Objective: Subject Questionnaire 1

To test the hypotheses for each questionnaire statement:

$$H_0: \Pr\{\text{subject response is at least 3, or “Neutral” to ‘Strongly Agree’}\} < 0.90$$

$$H_1: \Pr\{\text{subject response is at least 3, or “Neutral” to ‘Strongly Agree’}\} \geq 0.90$$

The minimum number of “successes”, X_c , to reject H_0 is determined such that $\Pr\{\text{Reject } H_0 | p=0.90\} \leq 0.95$.

[figure not shown]
Thus, with $n = 315$, $X_c = 276$, with power ≈ 0.9299 .

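### The ±12.5, protocol staff-test and Questionnaire 1 cut-offs reject the null about 93% of the time at its own boundary, so a pass does not show at least 95% (or 90%)

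*SAP*

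**What the plan says.** **±12.5 objective.** SAP 1.3 (people with diabetes, n = 315) and SAP 3.4 (n = 350, no population named) both put p < 95% under H0 and p ≥ 95% under H1. SAP 1.3 states that "the critical value is $X_c = 294$ yields a power to reject H_0 if" p = 0.95 of about 92.63%. SAP 3.4 states: "With $n = 350$, the critical value is $X_c = 327$ yields a power to reject H_0 if" p = 0.95, giving about 0.9246. In protocol 11.1 the critical value "is determined to be the smallest number such that" the chance of reaching it at p = 0.95 is no more than 0.95.

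**Staff test.** Protocol 11.1 (objective 2.2.9) applies the same rule to ±15 mg/dL or ±15%, with 294/315 and 327/350. SAP 3.4.1 instead applies the ISO criteria to people with diabetes and the FDA criteria to all subjects.

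**Questionnaire 1.** H0 is p < 90%. In SAP 7.1 the critical number "is a function of the actual sample size, and will be chosen such that" the pass probability at 90% is capped at 0.95. Protocol 11.3 concludes: "Thus, with $n = 315$, $X_c = 276$, with power" about 0.9299. Objective 2.2.3 requires at least a 90% probability of a score of 3 or more.

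**ISO and FDA criteria.** SAP 3.1 says "Symbolically, the ISO criterion is equivalent to testing the hypothesis" with boundary 96.79%. Protocol 11.2 says "These criteria, with $n = 350$, are equivalent to testing the hypotheses" with boundaries 0.9664 and 0.9960, and SAP 3.3 does the same. For ISO, protocol 11.1 uses 0.9678 and writes "The power to reject H0 at" that same value.

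No alpha is given for any of these tests.

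**The concern.** A test of H0: p < p0 needs a small rejection probability at p0, because p0 is the least favourable edge of the null. The plan makes it nearly 0.95. The rule therefore limits the risk of failing a device that is exactly on target. It does not limit the risk of passing one that is below target. Read as written, a pass rejects H0 and so concludes p ≥ 95% (or ≥ 90%), even when the observed percentage is itself below that figure.

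For the staff test there is a second problem: the two documents can return opposite verdicts on the same data.

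**Working it through.** **Inputs.** n, Xc and p0 come from SAP 1.3, 3.4 and 7.1 and protocol 11.1 and 11.3. The formula throughout is the exact binomial tail, Pr{X ≥ Xc | n, p} = Σ C(n,k) p^k (1−p)^(n−k), summed over k = Xc to n.

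**1. Reproducing the plan's figures.**

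| Rule | p0 | Pass mark | Pr{X ≥ Xc at p0} | Plan states |
|---|---|---|---|---|
| 294/315 | 0.95 | 93.3% | 0.9263 | 92.63% |
| 327/350 | 0.95 | 93.4% | 0.9246 | 0.9246 |
| 276/315 | 0.90 | 87.6% | 0.9299 | 0.9299 |

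Searching for the smallest Xc with a tail of at most 0.95 returns exactly 294, 327 and 276, so these are not misprints.

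**2. Type I error.** The tail is continuous and increasing in p, so its supremum over p < p0 equals its value at p0: 92.6%, 92.5% and 93.0%. At p = 0.949, inside H0, 294/315 still rejects with probability 0.9136.

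**3. Pass probability further inside H0.**

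| Rule | | | |
|---|---|---|---|
| 294/315 | p = 0.94: 73.8% | p = 0.93: 46.4% | p = 0.92: 22.5% |
| 327/350 | p = 0.94: 72.1% | p = 0.93: 42.8% | p = 0.92: 18.9% |
| 276/315 | p = 0.88: 62.4% | p = 0.87: 41.2% | p = 0.86: 23.0% |

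**4. What a bare pass supports.** The one-sided 95% Clopper-Pearson lower bounds at the pass marks are 90.5% (294/315), 90.8% (327/350) and 84.1% (276/315).

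**5. The same wording on the ISO and FDA criteria.** At their stated null boundaries, rejection is 0.9502 (300/315 at 0.9679), 0.9491 (300/315 at 0.9678), 0.9488 (333/350 at 0.9664) and 0.9466 (347/350 at 0.9960). These cut-offs come from observed-percentage rules and stand. Only the hypothesis wording is at fault.

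**6. Staff test, protocol against SAP.** In people with diabetes the protocol passes at 294/315, while the ISO rule in SAP 3.4.1 requires 300/315. At p = 0.95 the pass probability is 92.6% against 49.0%. At p = 0.94 it is 73.8% against 21.3%. For all subjects the accuracy definition differs too. The protocol uses ±15 mg/dL or ±15% with 327/350. The SAP uses the FDA ±15% (333/350) and ±20% (347/350).

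**7. Other conflicts.** The ±12.5 objective has n = 315 in people with diabetes in SAP 1.3 and protocol 11.1, but n = 350 in SAP 3.4. Protocol 2.2.8 is headed for people with diabetes, yet its double-asterisk footnote refers to all subjects. SAP 3.5 makes every critical value 95% of n, which fits neither 294/315 nor the 99% FDA criterion in SAP 1.2.

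**The case against.** - **The operating points are disclosed.** SAP Table 1.1 shows that ±12.5 passes 92.63% of the time at 95% and fails 94.64% of the time at 90.60%. The mock Questionnaire 1 table prints a critical percentage of 87.63%. This is fair: nothing is hidden. But Table 1.1 has no row for Questionnaire 1, the protocol's staff test or 327/350, and disclosure does not correct the direction of the inference.
- **Power is formally the right word at p0, because p0 lies in H1.** True, but the rejection probability just below p0 is practically the same, and that error is never stated.
- **The ISO and FDA relabelling changes no decision.** Correct. That part is editorial.
- **The 95% rule in SAP 3.5 and the n = 350 in SAP 3.4 are small slips.** Probably so. SAP 1.2 computes the 99% cut-off explicitly, and 327/350 matches the protocol's all-subject staff figure. Both still need correcting.
- **A stricter Questionnaire 1 rule may be dearer than single-statement power suggests.** Six statements carry pass/fail criteria. If all six had to pass and responses were independent, power at 293/315 would be 0.8063^6 ≈ 0.27 at p = 0.94 and 0.9536^6 ≈ 0.75 at p = 0.95. However, protocol 11.3 tests each statement, and SAP 3.5 evaluates each test without regard to the others. Single-statement power is therefore the relevant figure under the plan as written.

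On weight, the affected objectives are secondary. The ±12.5 and staff objectives are internal, Questionnaire 1 has no pass/fail criterion for FDA, and protocol 2.2 says that failing a sub-objective does not fail the secondary objective.

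**Conclusion.** The concern holds. The plan's arithmetic is right, but its hypotheses are the wrong way round for the rule it uses. With type I error reaching about 93% at the boundary, a pass supports only that the rate was not shown to be below 95% (or 90%). The calculations assume independent results with a common success probability, as the plan's Bernoulli framing does, and the sample sizes given in the plan.

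The staff-test conflict is the part that can change an outcome between documents: 294 to 299 of 315 passes one and fails the other. The primary ISO pass/fail decision does not change; only its hypothesis wording does. This should be fixed before reporting.

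**What to change.** **Preferred: text only.** Keep the ±12.5 and Questionnaire 1 cut-offs; the staff-test rule is settled under (c) below.
- Describe each as an acceptance rule, or restate as H0: p ≥ p0 against H1: p < p0. The boundary error is then 1 − 0.9263 = 7.4% (294/315), 1 − 0.9246 = 7.5% (327/350) and 1 − 0.9299 = 7.0% (276/315).
- Say that capping the pass probability at 0.95 forces this error above 5%. Holding it to at most 5% would give 293/315 (4.6%), 326/350 (4.9%) and 275/315 (4.95%).
- Drop the term power, report pass rates at lower p, and word a pass as not shown to be below 95% (90%). Align objectives 2.2.3, 2.2.8 and 2.2.9 with that wording.
- Relabel the ISO and FDA hypothesis statements in SAP 3.1 and 3.3 and protocol 11.1 and 11.2 in the same way, leaving 300, 333 and 347 alone.

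The cost is a weaker claim and no extra subjects.

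**Alternative, objective by objective, if a demonstration is wanted.** Keep H0 and H1, state an alpha, and take the smallest Xc whose tail at p0 is at most alpha. At an assumed one-sided 0.05 this gives 306/315 (tail 0.0449), 340/350 (0.0353) and, for Questionnaire 1, 293/315 (0.0404).
- Questionnaire 1: power per statement at 293/315 is 0.55, 0.81 and 0.95 at assumed p = 0.93, 0.94 and 0.95. No extra subjects are needed if p is about 0.94 or higher, and objective 2.2.3 could stand as worded.
- ±12.5: power at 306/315 is 0.19, 0.53 and 0.90 at assumed p = 0.96, 0.97 and 0.98. At p = 0.97, 80% power is first reached at n = 601 and holds consistently only from n = 694 people with diabetes (checked to n = 1499).

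**In either case:**
- (a) Give one population, n and Xc for ±12.5 in SAP 1.3 and 3.4, protocol 2.2.8 with its footnote, and protocol 11.1.
- (b) Say in SAP 3.5 that its 95% rule covers neither ±12.5 nor the FDA 20% criterion.
- (c) State one staff-test accuracy definition and cut-off for each population, identically in protocol 11.1 and SAP 3.4.1.

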3.1 ISO Objective

At least 95% of the glucose results obtained using the evaluation device must be accurate, namely:

$$-15\% \leq RD \leq +15\% \quad \text{LabBG} \geq 100\text{mg/dL}$$

OR

$$-15\text{mg/dL} \leq D \leq +15\text{mg/dL} \quad \text{LabBG} < 100\text{mg/dL}$$

As discussed in section 0 (Sample Size), with $n = 315$, the critical number (minimum) of accurate results is 300, which yields approximately a 95% chance of satisfying the ISO objective criterion if the actual probability that any result will be accurate is at least 96.79%. Symbolically, the ISO criterion is equivalent to testing the hypothesis:

$$H_0 : \text{Prob}\{\text{accurate}\} < 96.79\%$$

versus the alternative:

$$H_1 : \text{Prob}\{\text{accurate}\} \geq 96.79\%$$

There is approximately a 95% chance that the null will NOT be rejected if the actual probability that a result with the evaluation device would satisfy this definition of accuracy is only about 92.76%.

3.2 Venous Goal

Venous glucose results will be analyzed in the same fashion as the ISO accuracy objective for subject-generated capillary (fingerstick) results for only evaluable results from subjects with diabetes, and the same acceptance criteria applied.

3.3 FDA Objectives

3.3.1 95% within $\pm 15\%$

With $n = 350$, at least $X_c = 333$ measurements must be within $\pm 15\%$ of LabBG. This requirement is equivalent to testing the hypothesis:

$$H_0: \Pr\{|RD| \leq 15\% \} < 0.9664$$

against the hypothesis:

$$H_1: \Pr\{|RD| \leq 15\% \} \geq 0.9664$$

with $\Pr\{\text{reject } H_0 | p=0.9664\} \approx 0.9488$

3.3.2 99% within $\pm 20\%$

With $n = 350$, at least $X_c = 347$ measurements must be within $\pm 20\%$ of LabBG. This requirement is equivalent to testing the hypothesis:

$$H_0: \Pr\{|RD| \leq 20\% \} < 0.9960$$

against the hypothesis:

$$H_1: \Pr\{|RD| \leq 20\% \} \geq 0.9960$$

with $\Pr\{\text{reject } H_0 | p=0.9960\} \approx 0.9466$

3.4 Internal Accuracy Objective

The criterion is defined to be:

$|D| \leq 12.5 \text{ mg/dL}$ if $\text{LabBG} < 100 \text{ mg/dL}$, or:

$|RD| \leq 12.5\%$ if $\text{LabBG} \geq 100 \text{ mg/dL}$

The hypothesis:

$$H_0: \Pr\{\text{criterion met}\} < 95\%$$

will be tested against the alternative:

$$H_1: \Pr\{\text{criterion met}\} \geq 95\%$$

With $n = 350$, the critical value is $X_c = 327$ yields a power to reject H_0 if $\Pr\{\text{criterion met}\} = 0.95$ is ≈ 0.9246 .

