2.2.4 Fingerstick Test: Obtain T-PLUS BGMS performance data in the hands of **lay users with diabetes and naïve users** (without diabetes) from fingerstick capillary blood using Microlet NEXT lancing device.

- **95% of glucose results shall fall within $\pm 15\%$ of laboratory method across the entire tested range**
- **99% of glucose results shall fall within $\pm 20\%$ of laboratory method across the entire tested range**

2.2.5 Alternative Site Test (AST): Obtain T-PLUS BGMS performance data in the hands of **lay users with diabetes and naïve users** (without diabetes) from the palm site using the Microlet NEXT lancing device with the AST endcap. Acceptance criteria will be the same as fingerstick 2.2.4.

2.2.6 Samples will adequately span the claimed measuring range. At least ten unaltered samples with blood glucose concentration at the lower limits of the measuring range (less than 80 mg/dl) and at least ten unaltered samples at the upper limit measuring range (greater than 250 mg/dl) will be obtained for each anatomical site (i.e. fingerstick & palm).

2.2.7 Subject Questionnaire 1: The questionnaire will include statements about the T-PLUS BGMS instructions for use (product labeling) and ease of use of the basic blood testing operations of the meter system. These statements will be given a rating by all of the subjects (1=strongly disagree, 2=disagree, 3=neutral, 4=agree, 5=strongly agree), and frequency distributions will be tabulated. Results will be compared to the following criteria:

- **Acceptance criteria **: There will be no pass/fail criteria for FDA: SMBG 2018**

*This is a “total population” (hypothesis test) requirement for the pool of all subjects with diabetes.

** This is a “total population” (hypothesis test) requirement for the pool of all subjects (naïve and diabetic).

Study objectives 2.2.8 to 2.2.10 below are internal objectives and apply to data collected from all subjects OR subjects who have diabetes, as specified for each objective.

2.2.8 **Fingerstick Test (only subjects with diabetes):** Obtain T-PLUS BGMS performance data in the hands of lay users with diabetes using fingerstick capillary blood obtained with Microlet NEXT lancing device.

- **Test the hypothesis that there is at least a 95% probability that meter results would be within $\pm 12.5\text{mg/dL}$ of laboratory method at glucose concentrations $<100\text{ mg/dL}$ and within $\pm 12.5\%$ at glucose concentrations $\geq 100\text{ mg/dL}^{**}$**

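### SAP 3.4 gives the ±12.5 internal objective the all-subject planning figures (n=350, Xc=327) although the objective is for subjects with diabetes (n=315, Xc=294), leaving it unclear whose results count

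*SAP*

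**What the plan says.** Four places tie the ±12.5 objective to subjects with diabetes, in words or by their planning number.

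- Protocol 2.2.8 opens: "Fingerstick Test (only subjects with diabetes): Obtain T-PLUS BGMS performance data in the hands of lay users with diabetes".
- SAP 1.3 begins "For subjects with diabetes only (PWDs" and continues "With $n = 315$, the critical value is $X_c = 294$ yields a power to reject H_0", with a stated probability of about 92.63% at p=0.95.
- SAP Table 1.1 repeats 315 and 294 in its ±12.5 row.
- Protocol 11.1, under 2.2.8 Criterion 1, gives "For $n = 315$, $X_c = 294$ (power ≈ 0.9263". The same section explains 315 as the number of subjects with diabetes, 90% of 350.

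Two places point the other way.

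- SAP 3.4 repeats the criterion and both hypotheses of SAP 1.3, states no population, and gives "With $n = 350$, the critical value is $X_c = 327$ yields a power to reject H_0" with a probability of about 0.9246.
- The acceptance bullet of protocol 2.2.8 is marked with a double asterisk. The footnote for that marker reads: "This is a “total population” (hypothesis test) requirement for the pool of all subjects (naïve and diabetic". A single-asterisk footnote for the pool of subjects with diabetes exists in the same place and is not used here.

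In protocol 11.1 the pair 350/327 appears only under 2.2.9, the study-staff test with ±15 limits, which has an all-subject analysis as well as a diabetes-only one.

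**The concern.** The number 350 is not neutral. SAP 3.5 ties 315 to the ISO analysis, which uses subjects with diabetes, and 350 to the FDA analysis, which uses everyone. An analyst working from the Accuracy Analyses section of the SAP would find 350/327 and no instruction to leave out people without diabetes. An analyst working from the objective, or from SAP 1.3, would leave them out.

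These are different questions. The objective asks how the meter performs for lay users with diabetes; the pooled reading adds the 10 to 15% of subjects who do not have it. The result is a pass or fail on a stated hypothesis, so its population should be fixed in one form before the data are analysed.

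**Working it through.** **Inputs.** X is the number of results within limits, taken as Binomial(n, p). The boundary value is p = 0.95 (SAP 1.3 and 3.4, protocol 11.1). Protocol 11.1 sets Xc as the smallest number with Pr{X ≥ Xc | p = 0.95} ≤ 0.95. The planning n is 315 for subjects with diabetes (0.90 × 350) and 350 for all subjects.

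**Step 1: reproduce the plan's figures** (exact binomial upper tail).

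| n | Xc | Xc/n | Pr{X ≥ Xc} at 0.95 | Plan states | Pr at Xc − 1 |
|---|---|---|---|---|---|
| 315 | 294 | 93.33% | 0.9263 | 0.9263 | 0.9536 (293) |
| 350 | 327 | 93.43% | 0.9246 | 0.9246 | 0.9513 (326) |

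The last column exceeds 0.95 in both rows, so 294 and 327 are each the value the protocol's rule gives for that n. The arithmetic is sound. The two required proportions differ by about 0.1 percentage point.

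**Step 2: does the choice of population matter?** The diabetes-only rule allows 315 − 294 = 21 failures and the pooled rule 350 − 327 = 23. Take 350 evaluable results, of which 350 − 315 = 35 come from people without diabetes. The failure counts below are hypothetical.

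- 22 failures among the 315: 293 < 294, so the objective as headed fails. With 0 or 1 failure among the 35, the pool has 328 or 327 successes and passes.
- 23 failures among the 315: 292 < 294, fails. With none among the 35, the pool has 292 + 35 = 327 and passes.
- 21 failures among the 315: 294, passes. With 3 failures among the 35, the pool has 294 + 32 = 326 < 327 and fails.

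Near the boundary the two readings can disagree in either direction.

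**Step 3: the rule in SAP 3.5.** That section sets the critical value at 95% of the evaluable results, without exception.

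- 0.95 × 315 = 299.25, rounded up to 300. Pr{X ≥ 300 | 315, 0.95} = 0.490.
- 0.95 × 350 = 332.5, rounded up to 333. Pr{X ≥ 333 | 350, 0.95} = 0.515.

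Neither matches 294 or 327. For subjects with diabetes it would raise the mark by 300 − 294 = 6 results. Correcting the population in SAP 3.4 would therefore leave a second conflict in place.

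**Step 4: the staff test.** Moving 350/327 to the staff test does not settle matters. Protocol 11.1 gives 294/315 and 327/350 for 2.2.9. SAP 3.4.1 instead applies the ISO acceptance criteria (300 of 315) and the FDA criteria (333 and 347 of 350) to staff results.

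**The case against.** The strongest reply is that this is an editorial slip with a clear intended answer. Wherever a population is written out in the text of the objective or in the SAP, it is subjects with diabetes. The protocol introduces 2.2.8 to 2.2.10 by saying that the population is the one specified for each objective, so the 2.2.8 heading should govern. The double asterisk is a weak guide: it also sits on 2.2.9, whose heading calls for both an all-subject and a diabetes-only analysis. SAP 3.4 names nobody, so all subjects is an inference from n=350. This is also an internal secondary objective, and protocol 2.2 says that failing one sub-objective does not fail the secondary objective.

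All of that stands, and it limits the weight of the point. It does not remove it: to reach the intended answer a reader must set aside both SAP 3.4 and a protocol footnote.

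A reader might also infer that the trial is bound to a mark of 327 that 315 results could never meet. The documents do not support that. SAP 1.3 says that critical values depend on the actual sample size, so 294 and 327 are planning values to be recomputed. Recomputing them still requires knowing which subjects make up n.

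**Conclusion.** The inconsistency is real and should be corrected before analysis. It concerns population, not calculation: both printed pairs are correct for their own n, and the required proportions are 93.33% and 93.43%. What is at stake is whether about 35 results from people without diabetes enter a test written for people with diabetes, which can reverse the outcome when the failure count is within a few results of the limit.

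The size rests on the 10% share behind n=315. At 15% without diabetes, 0.15 × 350 = 52.5, leaving about 297 results from subjects with diabetes, and the limit of 21 failures would need recomputing. The documents give no failure rate for people without diabetes, so one cannot say that pooling would favour the device.

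A reader might infer that SAP 3.4 overrides SAP 1.3, or that the population was left open so that it could be chosen later. No text ranks one section over the other, and the 2.2.8 heading, protocol 11.1, SAP 1.3 and Table 1.1 agree in advance. The ISO and FDA acceptance decisions are not affected.

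**What to change.** 1. In SAP 3.4, state: subjects with diabetes only; n=315, Xc=294, probability of rejecting H0 at p=0.95 about 0.9263. Add that Xc is recomputed at the actual evaluable n as the smallest number with Pr{X ≥ Xc | p=0.95} ≤ 0.95.
2. On the protocol 2.2.8 bullet, replace the double asterisk with the single asterisk (pool of subjects with diabetes).
3. In SAP 3.5, limit the 95% rule to the objectives it covers, so that it no longer implies 300 of 315 for the ±12.5 test.
4. Reconcile the staff-test criterion as a separate item: decide whether 2.2.9 follows protocol 11.1 (294/315 and 327/350) or SAP 3.4.1 (ISO and FDA acceptance criteria), and write the same rule in both documents.

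The cost is wording in the SAP and protocol. Enrolment, procedures and data collection do not change.
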